2.2.1. Stratification

Randomization will be stratified by number of background pulmonary arterial hypertension (PAH) therapies into three distinct strata with Stratum 1 consisting of patients with no background PAH therapy, Stratum 2 consisting of patients with one background PAH therapy, and Stratum 3 consisting of patients with two background PAH therapies.

All patients in the study will follow the same visit and assessment schedule, shown in Figure 1. Following randomization, patients will be scheduled to be assessed in person during treatment at Weeks 1, 2, 4, 6, 8, 16, and 24 and by telephone contact on Days 3, 10, 21, 31, 38, 84, and 140. Patients will also be scheduled to be assessed at an in-person follow-up visit at Week 28, four weeks after the end of treatment.

Figure 1: Schema for study of bardoxolone methyl in patients with CTD-PAH

The number of administered doses will be calculated based on date of first dose, date of last dose, drug dispensed, and pill counts from drug returned. Patients who administer at least 126 doses (i.e., 75% of the 168 expected doses) will be considered treatment compliant. Patients who complete the study (i.e., complete study visits through Week 28), complete treatment (i.e., complete study medication through Week 24), and are considered treatment compliant will be eligible for a separate open-label extension study.

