5. GENERAL CONVENTIONS

The protocol-specified time windows for a visit ([Appendix D](#)) and time of a measurement (Section [5.4](#)) determine the visit assignment for each observation.

Continuous data will be summarized using descriptive statistics: number of observations (n), mean, median, standard deviation (SD), minimum, and maximum. Confidence intervals (CIs) will be presented as appropriate. The same number of decimal places as in the observed value will be presented when reporting minimum and maximum; 1 more decimal place than in the observed value will be presented when reporting mean and median; and 2 more decimal places than in the observed value will be presented when reporting SD. When values are averaged in the analysis data (e.g., in the calculation of baseline), the same number of decimal places as in the observed value will be presented.

Frequencies and percentages will summarize categorical data. Presentations of categorical data will generally suppress percentages for items where the count is zero in order to draw attention to nonzero counts.

Confidence intervals will generally be constructed at the 95% level. For binomial variables, exact methods will be employed unless otherwise specified.

Categorical/qualitative data will be presented using frequency counts and percentages. All percentages will be rounded to 1 decimal place, unless otherwise specified. Percentages equal to 100 will be presented as 100% and no percentages will be presented for zero frequencies.

Summary presentations will classify patients by their randomized treatment group for analyses on the ITT population, and actual treatment received for analyses on the safety population, unless otherwise specified. References to treatment group from this point forward in the SAP text indicate randomized treatment group, unless stated otherwise.

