5.4. Definition of time

For visits (or events) that occur on or after randomization, time is calculated in days as:

$$\text{time} = \text{visit (or event) date} - \text{date of randomization} + 1$$

For visits (or events) that occur prior to randomization, time is calculated in days as:

$$\text{time} = \text{visit (or event) date} - \text{date of randomization}$$

The quantity ‘days since first dose’ is defined as:

- days since first dose = visit (or event) date – date of first + 1

The quantity ‘days since last dose’ is defined as:

days since last dose = visit (or event) date - date of last dose For summaries that present distribution of time expressed in weeks and months, weeks will be defined as days divided by seven and months as days divided by 30.4375.

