10.2. Secondary efficacy outcome

The secondary efficacy outcome is the time-to-first persistent clinical improvement event. To declare that clinical improvement has occurred, at least one of the following four criteria must be met:

1. Improvement by at least one WHO functional class coupled with no more than a 15% decrease from baseline in 6MWT.
2. Increase from baseline in 6MWT by at least 10% and stability or improvement in the WHO functional class.
3. Decrease from baseline in creatine kinase (a surrogate biomarker for muscle injury and inflammation) by at least 10% and no worsening in WHO functional class and no more than a 15% decrease from baseline in 6MWT.
4. Improvement in estimated glomerular filtration rate (eGFR) $\geq 10\%$ of baseline.

The persistence of the change in WHO functional class, 6MWT, eGFR, or creatine kinase must be confirmed by a subsequent assessment that also meets the defined criteria. The confirmatory assessment must occur at least 14 days after the initial assessment, or at the next scheduled assessment. If persistent improvement is confirmed, the date of the event will be considered the initial assessment of improved WHO functional class, 6MWT, eGFR, or creatine kinase.

If confirmatory observation of initial improvement is not available for any reason, such as end of study or death, it may or may not be considered an event as defined by the timing of improvement as it relates to other study events. Below is a list of possible reasons for failure to obtain a confirmatory observation along with the adjustment to the definition of improvement.

These reasons are as follows:

1. Last visit: If the improvement is observed at the last scheduled assessment, the requirement for an additional assessment after 14 days is waived, and the patient is classified as satisfying the criteria for improvement. In the absence of study end date, Study Drug Termination (SDT) is used.
2. Death: If the patient's death occurs before the confirmatory observation, then the patient is classified as not satisfying the criteria for improvement.
3. Study termination: If the patient terminates the study for reasons of "lost to follow-up" or "withdrawal of consent", then the patient is classified as not satisfying the criteria for improvement.
4. Patient starts new PAH drug: If a patient decides to stop study drug and switch to a new PAH drug, then the patient is classified as not satisfying the criteria for improvement.

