11.2. Secondary efficacy outcome

The secondary efficacy outcome, the time to clinical improvement, will be analyzed using methods for a censored time-to-event outcome. All analyses will be stratified using number of background PAH medications at baseline to define the strata.

Summary tables will present median time to first clinical improvement and associated 95% CIs for each treatment group as well as hazard ratios and 95% CIs for each comparison of bardoxolone methyl to placebo. Median duration with appropriate 95% CIs, as well as the proportion of patients remaining event-free at times of interest, will be estimated using Kaplan-Meier methods with the product limit estimator computed using PROC LIFETEST in SAS.

PROC PHREG in SAS will be used to estimate hazard ratios, mean and standard error time -to-event, and their 95% CIs by Cox regression models.

[REDACTED]

In the event that the number of events across strata is too small, the strata consisting of zero background PAH medications and one background PAH medication will be collapsed.

[REDACTED]

[REDACTED]

Treatment group comparisons will use the Type 3 Chi-square test and unadjusted two-sided p-value associated with the treatment group variable in the Cox proportional hazards model. Time-to-event analyses will use Breslow's method of handling ties in event times [1], which is the default method used in PROC PHREG. The TEST statement in PROC LIFETEST will be used to include the strata and the STRATA statement will be used in PROC PHREG.

Kaplan-Meier plots will supplement these presentations. The number of patients within each treatment group at risk of an event at regular time points will appear at the bottom of these figures.

The secondary outcome is important in understanding the effectiveness of bardoxolone methyl and its ability to improve function.

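### Breslow tie handling for the visit-dated secondary endpoint pulls the hazard ratio slightly toward 1; Efron's method avoids this at no cost (minor)

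*SAP*

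**What the plan says.** SAP Section 11.2 compares the arms on time to first clinical improvement with a Cox model fitted in PROC PHREG. It states that "Treatment group comparisons will use the Type 3 Chi-square test and unadjusted two-sided p-value" for the treatment term will be used, and it names Breslow's "method of handling ties in event times [1], which is the default method used in PROC PHREG". No alternative tie method is visible. On strata it says: "All analyses will be stratified using number of background PAH medications at baseline to define the strata". The zero- and one-medication strata may be collapsed if events are few.

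Three other passages determine how many ties there will be:

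- **Event date.** SAP Section 10.2 says that, once improvement is confirmed, "the date of the event will be considered the initial assessment of improved WHO functional class, 6MWT, eGFR, or creatine kinase".
- **Visits.** SAP Section 2.2.1 says "patients will be scheduled to be assessed in person during treatment at Weeks 1, 2, 4, 6, 8, 16, and 24". SAP Section 11.1.1 lists the walk test at only four of these visits (Weeks 4, 8, 16 and 24).
- **Time scale.** SAP Section 5.4 says "For visits (or events) that occur on or after randomization, time is calculated in days as" the event date minus the randomization date plus 1. Protocol Table 3 gives these visits windows of plus or minus 3 days.

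**The concern.** An event can be dated only to a day on which the patient was assessed, and most such days cluster around seven visits. Many patients in the same stratum will therefore share an event time.

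For d tied events in a stratum, let S be the sum of risk scores over everyone at risk and D the sum over the tied patients. Breslow uses the denominator S^d. Efron uses the product over l = 0, …, d−1 of (S − (l/d)·D). The two agree when d = 1. When d is larger, Breslow keeps patients who have already had the event in every denominator. This over-represents the arm with more events, so the estimate moves toward no effect. The model standard error also exceeds the true spread of the estimate, which makes the test conservative.

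The hazard ratio, its confidence interval and the p-value of the only secondary efficacy endpoint all come from this model.

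**Working it through.** **Inputs from the documents.** N is about 130 and may rise to about 200, with 1:1 allocation (SAP Section 2.2). There are three strata, seven visits, windows of plus or minus 3 days, and time in actual days. Two-sided alpha of 0.05 is inferred from "Confidence intervals will generally be constructed at the 95% level" (SAP Section 5). The plan shows no hazard ratio, event count or power for this endpoint, so there is no planned figure to reproduce.

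**Assumptions.** True hazard ratio 1.0, 1.5 or 1.8; 40%, 70% or 85% of placebo patients with an event by Week 24; 10% dropout; strata shares of 10/40/50%; proportional hazards; events detected only at the seven visits.

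**Method.** A stratified Cox model with a Wald test was fitted with Breslow and with Efron to the same simulated trials (1,500 to 2,000 per scenario). Three patterns of visit dates were used:

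- evenly spread over the 7 in-window days;
- intermediate, with 44% of visits on the target day;
- all visits on the target day.

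**Calibration.** Schoenfeld power for 93 events at HR 1.5 is Φ(√(93/4) × ln 1.5 − 1.96) = Φ(4.822 × 0.4055 − 1.96) = Φ(−0.005) = 0.498. Efron with near-continuous dates also gave 0.498.

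**Results for N = 130, true HR 1.5, equal hazard per visit:**

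| Visit dates | Placebo events | Events tied | HR Breslow / Efron | Power Breslow / Efron | Loss (points) |
|---|---|---|---|---|---|
| Even spread | 40% | 39% | 1.485 / 1.489 | 29.9% / 30.6% | 0.7 |
| Even spread | 70% | 58% | 1.502 / 1.511 | 49.3% / 50.6% | 1.3 |
| Even spread | 85% | 67% | 1.481 / 1.495 | 52.0% / 54.4% | 2.4 |
| Intermediate | 40% | 51% | 1.499 / 1.506 | 31.0% / 31.9% | 0.9 |
| Intermediate | 70% | 66% | 1.485 / 1.500 | 46.7% / 49.0% | 2.3 |
| Intermediate | 85% | 72% | 1.466 / 1.489 | 48.9% / 52.7% | 3.8 |
| All on target | 40% | 93% | 1.470 / 1.495 | 29.1% / 31.6% | 2.5 |
| All on target | 70% | 97% | 1.436 / 1.491 | 39.5% / 48.1% | 8.6 |
| All on target | 85% | 97% | 1.416 / 1.501 | 41.7% / 55.5% | 13.8 |

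**Ranges over all scenarios with HR above 1:**

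- Even spread: power loss 0.2 to 2.4 points; largest HR gap 1.780 − 1.752 = 0.028.
- Intermediate: power loss 0.4 to 3.8 points; largest HR gap 1.784 − 1.741 = 0.043, at true HR 1.8 and 85% events. The cells for N = 200 at 85% were not completed.
- All on target: power loss 2.5 to 14.3 points.

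**Type I error.** With even spread, Breslow rejects 3.7% to 5.5% and Efron 4.1% to 5.7%. With all visits on target, Breslow rejects 1.7% to 4.4% and Efron 3.4% to 5.3%. One all-on-target null case (N = 130, 85% events) shows the mechanism. Breslow's mean model standard error is 0.197, but its estimates have a standard deviation of only 0.170. The effective critical value is 1.96 × 0.197/0.170 = 2.27, a two-sided rejection rate of about 2.3%; the simulated rate was 2.2%. Efron's figures are 0.197 and 0.192, with 4.9% rejection.

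**Sensitivity to early events.** Separate runs at N = 130 and HR 1.6, with 70% to 85% placebo events concentrated early, lost 2.6 to 3.8 points with even spread. With about 57% of visits on the target day they lost 3.8 to 9.5 points.

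**The case against.** The strongest objection is about size. A reader might infer from the seven-visit schedule that the plan gives up 10 points of power or more. The documents do not support that as the expected loss. SAP Section 5.4 counts actual days, the windows spread dates over up to 7 days, and stratification splits ties further. The rules in SAP Section 5.2 that attribute results to target visits concern scheduled measurements; nothing visible replaces event dates with nominal days. This part of the objection stands.

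A reader might also infer that events can occur only at the seven visits. That is too strong. Unscheduled visits include clinical chemistry (Protocol Section 9.7), whose panel covers creatine kinase and creatinine (Protocol Section 9.10.21), and SAP Section 5.2.1 accepts unscheduled laboratory results. Early-termination and Week 28 assessments add further dates. The simulations omit these and so may overstate ties somewhat.

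Nor does the text show that Breslow was chosen because it is the default. It describes the method as the default and cites a reference, without giving a reason.

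Parts of Section 11.2 are redacted, so a sensitivity analysis with another tie method may exist there. Finally, Breslow is a recognised, pre-specified method that errs on the conservative side. All of this limits the severity, but none of it favours Breslow over Efron.

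**Conclusion.** The point holds as a minor one. In every simulated scenario with a hazard ratio above 1, Breslow gave the estimate nearer 1 and the lower power, while Efron stayed close to the true value with type I error near 5%. On the SAP's own time scale the hazard ratio is generally about 0.01 to 0.03 lower (0.04 in the largest intermediate case), and the power loss is roughly 0 to 4 points. It approaches 10 points or more mainly when nearly all visits fall on the target day or nominal days are used, or when strong clustering combines with early events.

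Confidence is high in the direction and limited in the size, because the hazard ratio, event rates, event timing and date spread are all assumed. It would be wrong to infer a threat to the trial's main conclusion: type I error is not inflated, and the primary mixed model does not use this method.

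**What to change.** Before database lock and unblinding, replace Breslow with Efron in the tie-handling sentence of SAP Section 11.2 and set TIES=EFRON in PROC PHREG. Apply this to the secondary endpoint and to any other time-to-event analysis that the sentence governs. Data, model, strata and test are unchanged, so the cost is one sentence and one program option. Timing matters because SAP Section 1 treats analyses added after lock as ad hoc, and a later switch toward a larger estimated effect would look driven by the data.

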11.3. Exploratory efficacy outcomes

[Redacted]

11.3.1. Analysis of exploratory change from baseline endpoints

[Redacted]

[Redacted]

[Redacted]

[Redacted]

11.3.2. [Redacted]

[Redacted]

- [Redacted]
- [Redacted]
- [Redacted]
- [Redacted]

- [REDACTED]
- [REDACTED]
- [REDACTED]

[REDACTED]

11.3.3. Analysis of exploratory time-to-event outcomes

[REDACTED]

11.3.4. [REDACTED]

[REDACTED]

[REDACTED]

[REDACTED]

[REDACTED]

[REDACTED]

[REDACTED]

[REDACTED]

12. SAFETY ANALYSES

12.1. Safety variables

Safety variables will include physical examinations, vital sign measurements, ECG, clinical laboratory measurements, concomitant medications, AEs, and SAEs. The safety analyses will include all results collected from randomization through the end of the study. The safety analyses will include only patients in the safety population, with patients classified by whether they received any dose of bardoxolone methyl or not. For laboratory data, vital signs, and ECG data, On-treatment values will be summarized according to the analysis study windows and off-treatment values will be summarized according to the analysis study windows in [Appendix D](#).

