5.2.3. Last clinic visit and post-treatment results

Patients who terminate from the study before the Week 24 study visit should be brought back to the clinic as soon as possible for early termination assessments as well as a follow-up visit four weeks later. All assessments through Week 24 will be classified according to the time relative to randomization, regardless of the patient’s study participation or study drug status. Post treatment assessments will be classified according to the time relative to last dose in [Appendix D](#), for example 4 weeks off-treatment is within 7 to 35 days after last dose of the study.

Patients who discontinue treatment early but continue to be followed until the end of study will have their assessments attributed to visits as specified in [Section 5.2.1](#) and [Section 5.2.2](#).

A listing will indicate when each patient’s visits occurred. [Appendix D](#) indicates how scheduled results will be classified.

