12.3.3. Shift tables

Clinical laboratory test results categorized as in or out of the limits of the normal range will be summarized using “worst case shift tables,” that is, by cross-tabulating baseline result categories (high, normal, low) with worst case results during the treatment period. Shift tables will not be limited to results collected at scheduled visits, but will use all available results.

In addition, for ALT, AST and TBL, shift table summarizing (1) baseline to end of treatment, (2) baseline to worst on-treatment, (3) baseline to worst off-treatment, and (4) worst on-treatment to worst off-treatment will be presented.

12.4. 12-lead Electrocardiogram

All ECG measurements including ventricular rate, QT interval, Corrected QT interval - Fridericia’s formula (QTcF), and the overall interpretation will be displayed in a data listing. Only QTcF will be summarized. The QTcF will be calculated based on the following formula:

- $QTcF = QT / \text{cube-root}(\text{RR interval})$
- $RR \text{ interval} = 60 / \text{heart rate}$

A summary table of the actual values and change from baseline will be presented for QTcF by treatment group. In addition, the categories for QTcF of: ≤ 450 msec, $> 450 - 480$ msec, $> 480 - 500$ msec, and > 500 msec, and categories of change from baseline for QTcF of: ≥ 30 msec and ≥ 60 msec will be summarized by visit and treatment group.

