APPENDIX D. CLASSIFICATION OF VISITS

Table D 1. Classification of on treatment visits

Timing of assessment (days relative to first dose of study drug ^a)	Target day	Visit associated with assessment
1	1	Day 1 ^a
2 to 10	7	Week 1
11 to 21	14	Week 2
22 to 35	28	Week 4
36 to 49	42	Week 6
50 to 84	56	Week 8
85 to 139	112	Week 16
140 to 182	168	Week 24 ^a
7 ≤ Days after last dose ≤ 35	28	Week 28 ^c

^a Day 1 is the day of first dose of study drug.

^b Week 24 values is the average of the two values closest to target date.

^c Week 28 is only applicable to eGFR change from baseline efficacy analysis

Table D 2: Analysis Visits for Post-Treatment Safety Analysis

Analysis Visit	Label	Target Study Day (Reference Day is Days After Last Dose)	Analysis Window
40	4-weeks – Off Treatment	28	$7 \leq \text{Study Day} \leq 35$
80	8-weeks – Off Treatment	56	$36 \leq \text{Study Day} \leq 63$
120	12-weeks– Off Treatment	84	$64 \leq \text{Study Day} \leq 91$
240	24-weeks– Off Treatment	168	$92 \leq \text{Study Day} \leq 175$

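### The SAP sets no last-dose boundary for on-treatment laboratory, vital-sign and ECG values, so off-drug values of retained early stoppers enter on-treatment summaries and many also qualify as off-treatment

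*SAP*

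**What the plan says.** SAP Section 12.1 covers laboratory, vital-sign and ECG data with one sentence. It states "On-treatment values will be summarized according to the analysis study windows", then makes the same provision for values off treatment and points to Appendix D. It defines neither status.

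Appendix D has two tables with different clocks.

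- "Table D 1. Classification of on treatment visits" has the time column "Timing of assessment (days relative to first dose of study drug". Its rows run from Day 1 to Week 24 (Days 140 to 182), and none of them stops at last dose. A further Week 28 row is reserved for the eGFR efficacy analysis.
- Table D 2, for post-treatment safety, has the reference column "Target Study Day (Reference Day is Days After Last Dose". Its windows are 7–35, 36–63, 64–91 and 92–175 days, with targets 28, 56, 84 and 168. It does not exclude records already placed by Table D 1.

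Section 5.2.3 adds "All assessments through Week 24 will be classified according to the time relative to randomization", and says that this holds whatever the patient's study drug status. It sends the assessments of patients who stop drug but stay in follow-up to the ordinary visits. It also classifies post-treatment assessments by time since last dose, without limiting this to records after Week 24. Section 12.3 applies Sections 5.1 to 5.3 to the laboratory summaries.

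Section 12.3.3 plans, for ALT, AST and total bilirubin, a shift table from "worst on-treatment to worst off-treatment", and says that shift tables use all available results rather than scheduled visits only.

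Protocol Section 8.4.1 asks patients who stop study drug to continue all visits where possible, so off-drug records during the 24 weeks are expected.

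**The concern.** A summary labelled on-treatment should describe patients exposed to drug. Here the label follows the calendar, so a value taken weeks after the last dose counts as on-treatment if it falls before Day 183. The same record can then meet a Table D 2 window.

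Stopping is not unrelated to these measurements: Protocol Section 8.4.1 makes certain transaminase elevations a reason to discontinue. The misclassified records therefore come partly from the patients of most interest for safety. At stake are the comparison of liver tests on and after drug, the QTcF summary at Week 24, and by-visit means at the later visits. The primary efficacy analysis is not touched.

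**Working it through.** The plan gives no figure on this point to reproduce. The check is to apply both tables to the scheduled visits (Days 7, 14, 28, 42, 56, 112, 168 and 196, Protocol Table 3). Randomization and first dose are both taken as Day 1, because Table D 1 counts from first dose and Section 5.2.3 from randomization.

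**Step 1. One patient, last dose on Day 45, who stays in the study.** Days after last dose = visit day − 45.

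| Visit | Days after last dose | Table D 1 | Table D 2 | Selected for the off-treatment row? |
|---|---|---|---|---|
| Day 56 | 56 − 45 = 11 | Week 8 (50–84) | 4 weeks (7–35) | Yes, only scheduled visit in the window |
| Day 112 | 112 − 45 = 67 | Week 16 (85–139) | 12 weeks (64–91) | Yes, only scheduled visit in the window |
| Day 168 | 168 − 45 = 123 | Week 24 (140–182) | 24 weeks (92–175) | Not if Day 196 is attended |
| Day 196 | 196 − 45 = 151 | none for safety | 24 weeks (92–175) | Yes |

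The last column uses the closest-to-target rule of Sections 5.2.1 and 5.2.2. In the 24-week window, Day 168 lies 168 − 123 = 45 days from target and Day 196 lies 168 − 151 = 17 days from target, so Day 196 is used. Days 56 and 112 are thus tabulated in both periods. Day 168 counts as Week 24 on-treatment, 123 days after the last dose.

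**Step 2. All last-dose days.** For every last dose from Day 1 to Day 161, at least one scheduled off-drug visit through Week 24 falls in both tables. The limit is 161 because 168 − 161 = 7, the first day of Table D 2.

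| Last dose | Off-drug visits through Week 24 | Of these, in both tables |
|---|---|---|
| Day 14 | 5 | 5 |
| Day 28 | 4 | 4 |
| Day 56 | 2 | 2 |
| Day 112 | 1 | 1 |

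For last dose on Day 28, the off-drug days up to Day 182 number 182 − 28 = 154. Both labels apply from Day 35 to Day 182, which is 148 days. The other 6 are the days just after last dose, where Table D 2 has not yet begun.

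**Step 3. The worst-value shift table.** Because this table uses all results, closest-to-target selection does not thin the overlap. If every record to Day 182 counts as on-treatment, then every off-treatment record to Day 182 is also in the on-treatment set. The worst on-treatment value is then at least as bad as the worst off-treatment value over those records. A worsening after drug can show as a shift only through a record after Day 182. An elevation that first appears off drug before then is credited to both periods and lands in a no-change cell.

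**Step 4. ECG.** Protocol Table 3 schedules post-baseline ECGs only at Week 24 (or end of treatment) and Week 28. For a retained early stopper the Week 24 ECG is off drug, yet it enters the on-treatment QTcF summary.

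**Step 5. By-visit means.** If a share p of the values at a visit is off drug and these keep a fraction r of a mean drug effect, the summary shows 1 − p(1 − r) of that effect. The documents give neither p nor r. As an assumption only, p = 10–20% gives an understatement of 10–20% at r = 0 (full reversal), 5–10% at r = 0.5, and none at r = 1.

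**The case against.** The best reply is that Section 12.1 splits values by drug status first and applies windows second, so each record already has one status. Table D 1 also serves efficacy, where ignoring drug status is proper. A Table D 2 start at day 7 fits an intended partition at last dose plus 6 days. This reading is possible, but it rests on a term the SAP never defines and conflicts with Section 5.2.3, which Section 12.3 imports for laboratory data. Only adverse events have a last-dose limit (30 days, Section 12.2).

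Several limits on the point do stand, and a reader might otherwise infer more than the documents support.

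- *Every off-drug record is tabulated twice.* Not so: the selection rule removes some from the by-visit rows, as Day 168 shows.
- *The shift table hides on-drug elevations.* Not so: adding recovered values cannot lower a worst on-treatment value. The error arises only when the worst result comes after stopping.
- *Weight is misclassified in the same way.* The Section 12.1 sentence does not name weight, and Section 12.5 summarizes it by scheduled visit.
- *Transaminase threshold counts are affected.* Section 12.3.1 counts them at any time during the study, so they are not.
- *Late liver-test and magnesium means are heavily diluted.* Protocol Section 5.1.3 says transaminase rises mostly resolve while drug continues, and Section 5.1.6 says the magnesium decrease attenuated after 8 weeks. The late effect open to dilution may be small.

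A by-visit summary regardless of drug status is also a legitimate analysis. The fault lies in labelling it on-treatment.

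**Conclusion.** The point holds as a defect of classification in the descriptive safety analyses. It does not depend on any assumed rate: the overlap follows from the two tables and Section 5.2.3 for any retained patient whose last dose is on or before Day 161 and who attends the scheduled visits.

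The ALT, AST and bilirubin comparison of worst on-treatment with worst off-treatment suffers most. Week 24 QTcF and late by-visit laboratory and vital-sign means are affected as well. How many patients this involves, and how far any mean moves, cannot be computed, because the documents state no early-stop rate and no degree of reversal. The 10–20% range above is an illustration and should not be read as an estimate. The SAP should be corrected on this point, but the primary conclusion of the trial does not turn on it.

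**What to change.** Add to SAP Section 12.1 a definition for laboratory, vital-sign and ECG safety data: on-treatment records run from first dose through a stated cut-off after last dose, and the cut-off meets the start of Table D 2. Last dose plus 6 days does this and gives zero overlap for every last-dose day. Another justified cut-off would serve if Table D 2 is moved to match.

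Apply the definition to every safety summary labelled on-treatment and to worst on-treatment in Section 12.3.3. Assign later records only to Table D 2. State how temporary dose interruptions are counted, and that the 30-day adverse-event rule is a separate boundary. Leave the efficacy windows unchanged.

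The cost is a short SAP text and a date flag. The real downside is that on-treatment counts fall at late visits and the means then describe patients still on drug, a group selected in part by tolerance. For that reason keep a by-visit summary regardless of drug status, under its own label.
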